http://www.fda.gov/ohrms/dockets/AC/04/briefing/4028B1_05_NIH-Inclusion%20of%20Children.doc http://www.hhs.gov/ohrp/policy/populations/children.html

Studies that exclude children must have appropriate justification. Please select all that apply:

Phase I or Phase II study targeting cancer that is very unusual in pediatrics (e.g., prostate, lung, breast, chronic lymphocytic leukemia, etc.)

Are	participan	ts >65 years	s of age eligible t	o participate in th	nis study?		Yes	\bigcirc	No
	pa:	to ve your	, e. age engiale i			-		\sim	

Are pregnant women eligible to participate in this study? O Yes • No

Will the recruitment population at M. D. Anderson include persons who are incarcerated at time of enrollment (e.g., prisoners) or likely to become incarcerated during the study? ○ Yes ● No

Disease Group:

Lymphoma

Treatment Agents/Devices/Interventions:

Carfilzomib

Proposed Treatment/Study Plan:

Is treatment assignment randomized?	Yes	lacksquare	No
-------------------------------------	-----	------------	----

Is this a blinded or double-blinded study? \bigcirc Y	es		No
---	----	--	----

This will be a single-center, phase II clinical trial in patients with relapsed refractory mantle cell lymphoma.

Carfilzomib will be given at a dose of 20*/56 mg/m² (* CFZ 20 mg/m² IV on Days 1 and 2 in Cycle 1 followed by 56 mg/m² for each subsequent dose thereafter) on days 1 and 2, 8 and 9, 15 and 16 of a 28-day cycle (following cycle 12 carfilzomib will be given on days 1 and 2 and 15 and 16 only). The targeted enrollment according to our statistical design is 60 patients.

All patients shall be registered with CORe (Clinical Oncology Research System) at [contact] prior to receiving therapy.

Carfilzomib will be administered intravenously (IV) at $20/56 \text{ mg/m}^2$.

Overall response rate (ORR) (\geq partial response [PR]) will be assessed by the Revised Response Criteria for Malignant Lymphoma, with secondary assessment of clinical benefit response (CBR = minimal response [MR] + ORR), time to progression (TTP), and duration of response (DOR).

Therapy will continue in 28-day cycles for a maximum of 36 cycles (3 years), until there is disease progression, unacceptable toxicity or the patient chooses to withdraw from therapy.

All patients will be asked to record the medications they take at home and to bring the medication record they use to the clinic with them when they return to see their physician or

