- 5. Hematology: hemoglobin, hematocrit, WBC with complete manual differential (neutrophils [segmented and bands], lymphocytes, monocytes, eosinophils, basophils), RBCs, platelet count (for screening, historical panel may be used if within 14 days prior to initiation of therapy). Obtain and review prior to each dose of carfilzomib on days 1, 8 and 15 of Cycles 1 and 2 and on days 1 and 15 of Cycle 3. Obtain and review prior to dosing on day 1 of each subsequent cycle and as clinically indicated.
- 6. Full blood chemistry panel: BUN, creatinine, glucose, uric acid, bicarbonate, calcium, chloride, phosphorus, potassium, sodium, albumin, total protein, magnesium, total bilirubin, alkaline phosphatase, ALT, AST, LDH (for screening, historical panel may be used if within 14 days prior to 1st day of study drug). Repeat on days 8 and 15 of cycle 1 and on days 1 and 15 of cycle 2 and 3, thereafter repeat on day 1 of each subsequent cycle. Serum β2 microglobulin, Hepatitis B and C at baseline.
- Coagulation tests: prothrombin time, activated partial thromboplastin time, and international normalized ratio (historical panel may be used if within 14 days prior to 1st day of study drug)
- 8. Pregnancy tests for FCBP. Does not have to be performed on C1D1.
- A female of childbearing potential (FCBP) is a sexually mature woman who: 1) has not undergone a hysterectomy or bilateral oophorectomy; or 2) has not been naturally
 postmenopausal for at least 24 consecutive months (i.e., has had menses at any time in the preceding 24 consecutive months).
- 10. Disease Assessment: Obtain bi-dimensional measurements. The same method of assessment and the same technique should be used to characterize each identified and reported lesion at baseline and during follow-up.
- 11. A formalin-fixed paraffin embedded tumor block or slides must be sent MD Anderson's pathology department for confirmation of MCL diagnosis. However, prior to enrollment, a report from a local laboratory is acceptable. Not needed for patients with non-measurable disease. The Investigatorcan determine whether or not a tumor biopsy is needed.
- 12. Starting in Cycle 3, repeat every 2 cycles up to cycle 12 and then every 3 cycles. Perform only those evaluations with known or suspected sites of disease. If no change in persistent mass, a biopsy is to be performed if feasible.

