- 13. Send baseline bone marrow aspirate for cytogenetics and lymphoma markers. FISH for IgH/cyclin D1 may be required to make a definitive diagnosis if bone marrow is inconclusive. Repeat only if initially positive and send bone marrow aspirate for lymphoma markers. Repeat bone marrow biopsy to confirm CR.
- 14. Baseline colonoscopy and other GI endoscopies are required only if this is the main area of disease response assessment. They do not need to be repeated on C1D1. If in CR by radiologic evaluation, bone marrow or blood test at any time, do colonoscopy with random biopsy and bone marrow biopsy and PET scan if necessary and possible to confirm CR.
- 15. Carfilzomib administration: See section 6 for pre-treatment therapy and study drug administration and section 7 for dose modification guidelines.
- 16. Approximately 30 days after discontinuation of all study drugs or before start of subsequent treatment (whichever occurs first)
- 17. Every 6 months for 1 year via telephone. For subjects who did not progress during treatment.
- 18. ECHO/MUGA can be done as needed at any other time with cardiac consultation. They do not need to be repeated on C1D1.

Study Enrollment:

The study population for this research will consist of participants from:

Only at MDACC

Estimated Accrual:

Total Accrual at MDACC:	60
Estimated monthly accrual at MDACC:	1-2

Accrual Comments:

Is this an NCI-Cancer Therapy Eval	on Protocol (CTEP)? No
------------------------------------	------------------------

Is this an NCI-Division of Cancer Prevention Protocol (DCP)? No

Statistical Considerations:

The primary objective for this phase II study is to estimate the efficacy and evaluate the toxicity

of the single agent Carfizomib when given to patients with relapse/refractory mantle cell lymphoma (MCL). The maximum number of patients will be enrolled is 60.

The overall response (OR: complete response + partial response) at 4 cycles and toxicity at 1 cycle will be monitored simultaneously using the Bayesian stopping boundaries calculated based on beta-binomial distribution. Independence is assumed between OR and toxicity. Toxicity is defined as the following toxicities observed during cycle 1 (28 days) of the treatment:

Non-hematologic:

- >/= Grade 2 neuropathy with pain
- >/=Grade 3 non-hematologic toxicity (excluding nausea, vomiting, diarrhea, hyperglycemia due to dexamethasone treatment and rash due to lenalidomide treatment)

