- >/=Grade 3 nausea, vomiting, or diarrhea uncontrolled by maximal antiemetic/antidiarrheal therapy
- >/=Grade 4 fatigue persisting for > 7 days
- Treatment delay greater than 21 days for toxicity

Hematologic:

- Grade 4 neutropenia [absolute neutrophil count (ANC) < 500/mm3] lasting for > 7 days
- Febrile neutropenia (ANC < 1,000/mm3 with a fever >/= $38.3 \cdot \text{C}$)

Grade 4 thrombocytopenia (<25,000/mm3) that persists for >/= 7 days, despite holding treatment Treatment delay greater than 21 days for toxicity

Based on the efficacy and toxicity data from a Phase II study of Velcade in relapse/refractory MCL and two Phase II ongoing studies of Carfizomib in multiple myeloma, we will consider that Carfizomib is promising in treating relapse/refractory MCL if the OR rate at 4 months is at least 45% and the toxicity rate at 1 month is below 30%. A sample size of 60 ensures that, if the trial is not terminated early, a posterior 90% credibility interval for OR ate at 4 months will have width of .21 at most, under the assumption of a 45% OR rate. The prior probabilities of OR and toxicity for the regimen are modeled by beta distributions (*Beta*(0.9, 1.1) and *Beta*(0.6, 1.4), respectively). Denoting the probabilities of OR and toxicity by $\{\theta_{OR}, \theta_{TOX}\}$, and they are compared to fixed targets of OR and toxicity rates. The following decision criteria will be applied:

- 1) stop if Prob{ $\theta_{OR}\!<\!0.45\,|\,data\}\!>\!0.95,$ and
- 2) stop if Prob{ $\theta_{TOX} > 0.30 | data$ } > 0.95

Patients will be monitored by a cohort size of 10 according to the following stopping boundaries for OR at 4 months and toxicity at one month. If the number of responses required for moving the trial to next stage has not been achieved, the patient enrollment will be halted until enough responses observed.

Number of patients evaluated	Stop if ≤ OR observed	Stop if \geq toxicity observed		
10	1	б		
20	5	10		
30	8	14		
40	12	18		
50	16	21		
60	Always stop with this many patients			

The operating characteristics are summarized in the following tables (based on simulations from 10,000 trials).

True Toxicity Rate	True OR Rate	Prob(stop the trial early due to toxicity or futility)
0.10	0.25	0.928
	0.35	0.493
	0.45	0.103
	0.55	0.011
	0.65	0.001
0.20	0.25	0.928
	0.35	0.497
	0.45	0.111
	0.55	0.020
	0.65	0.009
0.30	0.25	0.936
	0.35	0.551
	0.45	0.206
	0.55	0.125
	0.65	0.116
0.40	0.25	0.967
	0.35	0.766
	0.45	0.587
	0.55	0.544

	0.65	0.539
0.50	0.25	0.995

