	0.35	0.962
	0.45	0.932
	0.55	0.926
	0.65	0.925

The above stopping boundaries and operating characteristics are calculated using MultcLean (v.2.0.0) design software downloaded from http://biostatistics.mdanderson.org/SoftwareDownload. A sample size of 1000 was used for the historical (standard treatment) data for the Model Input to approximate the fix targets for OR and toxicity rates.

Summary statistics will be provided for continuous variables. Frequency tables will be used to summarize categorical variables. Logistic regression will be utilized to assess the effect of patient prognostic factors on the response rate and the toxicity rate. The distribution of time-to-event endpoints including overall survival and progression free survival will be estimated using the method of Kaplan and Meier. Comparison of time-to-event endpoints by important subgroups will be made using the log-rank test. Cox proportional hazard regression will be employed for multivariate analysis on time-to-event outcomes.

Toxicity data will be summarized by frequency tables for all patients. For the efficacy endpoints, intend-to-treat analysis will be applied to the eligible patients. For the toxicity endpoint, per-treated analysis will be performed to include any patient who received the treatment regardless of the eligibility nor the duration or dose of the treatment received.

Data Safety Monitoring Board / DSMB at MDACC:

Select the name of the data safety monitoring board (DSMB) monitoring this protocol: Not Applicable

Please explain: This protocol is not randomized or blinded.

Protocol Monitoring:

Does this protocol have a schedule for interim and final analysis? Yes

Provide a summary or schedule of interim analysis.

Patients will be monitored by a cohort size of 10 according to the following stopping boundaries for OR at 4 months and toxicity at one month. If the number of responses required for moving the trial to next stage has not been achieved, the patient enrollment will be halted until enough responses observed.

Number of patients evaluated	Stop if = OR observed</th Stop if >/= toxicity observed	Stop if >/= toxicity observed
10	1	6
20	5	10
30	8	14
40	12	18
50	16	21
60	Always stop with this many patients	

Protocol Monitoring Plan:

This study will be monitored by the MD Anderson IND Office and a protocol-specific monitoring plan will be followed.

Intellectual Property:

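### Does the wording that enrollment is halted until enough responses are seen undo the futility stop?

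*Combined protocol and SAP*

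**What the plan says.** Statistical Considerations fixes what is monitored: "The overall response (OR: complete response + partial response) at 4 cycles and toxicity at 1 cycle will be monitored simultaneously". Criterion 1 stops the trial when the posterior probability that the response rate is below 0.45 exceeds 0.95. The boundary table, indexed by the number of patients evaluated, heads its efficacy column "Stop if ≤ OR observed" and gives limits of 1, 5, 8, 12 and 16 responses at 10, 20, 30, 40 and 50 patients.

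The text just above that table introduces the boundaries as applying to response at 4 months and toxicity at one month. It then adds that, if the responses needed for the next stage have not been reached, "the patient enrollment will be halted until enough responses observed". The same sentence and table recur under Protocol Monitoring. Neither place says how long the halt may last. No halt wording is attached to toxicity.

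**The concern.** A stop is final, whereas a halt until something happens is conditional. Once every patient in a cohort has been evaluated and accrual is closed, the only new responses that could appear are late ones in the same patients.

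The trial would observe such responses. Treatment may run to 36 cycles (Proposed Treatment/Study Plan), and note 12 of the Table of Assessments schedules CT thus: "Starting in Cycle 3, repeat every 2 cycles up to cycle 12 and then every 3 cycles". At 1 to 2 patients per month, the first and tenth patients of a cohort enter 9/2 = 4.5 to 9/1 = 9 months apart, so scans beyond cycle 4 would already exist at the first look.

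If those responses could lift the halt, the futility rule would be weaker than the operating-characteristics table states, and the error would always favor continuing an agent below the 45% target.

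**Working it through.** **Inputs, all from Statistical Considerations.** Looks at 10, 20, 30, 40 and 50 patients. Futility limits 1, 5, 8, 12, 16 (stop at or below). Toxicity limits 6, 10, 14, 18, 21 (stop at or above). Response and toxicity are independent. The operating-characteristics table has 25 scenarios.

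**Step 1: which action does the stated table assume?** Let X be the running number of responses. At each look, add a Binomial(10, p) increment, remove the probability mass at or below the limit as permanently stopped, and carry the rest forward. Do the same for toxicity with the mass at or above its limit. Then

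P(early stop) = 1 − (1 − P_futility)(1 − P_toxicity).

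Cumulative futility stopping by look:

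| True response rate | n=10 | 20 | 30 | 40 | 50 |
|---|---|---|---|---|---|
| 0.25 | 0.244 | 0.633 | 0.745 | 0.862 | 0.928 |
| 0.35 | 0.086 | 0.265 | 0.324 | 0.412 | 0.493 |
| 0.45 | 0.023 | 0.066 | 0.076 | 0.090 | 0.103 |

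Toxicity stopping alone is 0.0002, 0.009, 0.115, 0.539 and 0.925 at true rates 0.10 to 0.50. Two combined examples:

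- Response 0.25, toxicity 0.10: 1 − (1 − 0.9277)(1 − 0.0002) = 0.928; stated 0.928.
- Response 0.35, toxicity 0.30: 1 − (1 − 0.4927)(1 − 0.1148) = 0.551; stated 0.551.

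All 25 cells agree, with a largest difference of 0.0005. The design was therefore evaluated with a permanent stop and each patient counted once.

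**Step 2: does the halt sentence contradict that?** Put the pieces in order. The boundaries are for response at 4 months, the rows count patients evaluated, and the required number of responses refers back to those boundaries. With 1 to 2 patients per month and a 4-month endpoint, about 1 × 4 = 4 to 2 × 4 = 8 patients are still unevaluated when a cohort fills. The sentence tells the site not to enroll the next cohort meanwhile. Two outcomes are possible:

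- The count passes the limit before everyone is evaluated. Accrual resumes. The decision is the same as at full evaluation, because a count of responders cannot fall as more outcomes arrive.
- Everyone is evaluated and the count is at or below the limit. No further 4-month response can occur, so the condition for lifting the halt cannot be met, and criterion 1 stops the trial.

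Either way, the trial continues or stops exactly as in Step 1.

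**Step 3: what would the other reading cost?** Assume a share c of 4-cycle non-responders respond later and are counted. The documents give no such rate, so c is an assumption. The ever-response rate is q = p + c(1 − p), and the recursion is rerun with q:

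| p | c | q | Futility stop |
|---|---|---|---|
| 0.25 | 0.02 | 0.265 | 0.889 |
| 0.25 | 0.05 | 0.2875 | 0.809 |
| 0.25 | 0.10 | 0.325 | 0.628 |
| 0.35 | 0.02 | 0.363 | 0.424 |
| 0.35 | 0.05 | 0.3825 | 0.328 |
| 0.35 | 0.10 | 0.415 | 0.197 |

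The baselines are 0.928 and 0.493.

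**Step 4: how much hangs on one response?** Of futility stops, 54.8% at p = 0.25 and 66.1% at p = 0.35 are exactly one response short. Suppose each of these trials were handed one late response with certainty and then met the remaining boundaries as permanent stops. At p = 0.25, 87% of them would stop anyway, and total stopping would fall from 0.928 to 0.863. At p = 0.35, 54% would stop anyway, and the total would fall from 0.493 to 0.342.

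**The case for a change.** The strongest case for a change is that the pause reading is inferred. No sentence says that a halt ends in closure or that later responses are excluded. Late scans will be on file at the first look, no data monitoring board is assigned, and the protocol-specific monitoring plan is not among the documents. One added sentence would settle the matter without touching the boundaries or the sample size.

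What stands is that the end of the halt is unwritten, and that the published probabilities would not describe a trial that counted late responses. What does not stand is that the plan offers that option. Continued treatment and scanning show only that late responses could be seen; nothing brings them into the monitored count, which is tied to a time point in the endpoint definition, the target and the boundaries. The large share of near misses also overstates the stakes, because most such trials at a response rate of 0.25 would stop at a later look (Step 4).

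A tighter sentence could also do harm. Under note 12 the scan that reads out four completed cycles falls around day 1 of cycle 5, so a bare exclusion of anything first seen after 4 cycles might discard the scan the endpoint needs. Which patients form the interim denominator is a separate question.

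**Conclusion.** The concern does not call for a change. The sentence is loosely worded, but its evident purpose is to hold accrual while 4-cycle outcomes mature. The rest of the section supplies the ending: after full evaluation, a count at or below the limit is a stop. On that reading the effect on the operating characteristics is zero, and the 25 stated probabilities hold to within 0.001. The reductions in Step 3 need two things that the plan does not supply: counting responses beyond the monitored time point, and an assumed late-response rate. Toxicity stopping is unaffected on either reading. The conclusion rests on taking the stated 4-cycle or 4-month endpoint at its word and on the table's rows meaning patients with a known outcome. This is a gap that a trial statistician running the interim looks would fill correctly.
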